5.2.1. Analyses for Binary Endpoints

5.2.1.1. Cochran-Mantel Haenszel (CMH) Approach

For a single time point (eg, ASAS20 response rate at Week 16), difference in response proportion between tofacitinib 5 mg BID and placebo groups will be estimated using the Cochran-Mantel Haenszel (CMH) approach adjusting for stratification factor of prior treatment history (strata of "bDMARD-naïve" and "TNFi-IR or bDMARD Use [Non-IR]") (Cochran, 1954; Mantel and Haenszel, 1959).^{3,4} Large sample approximation will be used for testing the superiority of tofacitinib 5 mg BID to placebo at Week 16 and prior time points and for forming 95% CI's and calculating p-values. This approach will be referred to as CMH.

Explicitly, let \hat{p}_{Ai} and \hat{p}_{Bi} represent the estimated response rates for tofacitinib 5 mg BID (A) and placebo (B), respectively, of the i^{th} stratum. Using the CMH weights, the weighted difference in proportions between tofacitinib 5 mg BID and placebo groups, d, is expressed by:

$$d = \sum_i w_i (\hat{p}_{Ai} - \hat{p}_{Bi})$$

where $w_i = \frac{(n_{Ai}n_{Bi})/(n_{Ai}+n_{Bi})}{\sum_i (n_{Ai}n_{Bi})/(n_{Ai}+n_{Bi})}$, is the CMH weight for the i^{th} stratum, with n_{Ai} and n_{Bi}

equal the numbers of subjects in the tofacitinib 5 mg BID and placebo groups, respectively, per stratum. The weights are normalized such that the sum across strata adds up to 1.

The variance of d is:

$$\text{var}(d) = \sum_i w_i^2 \text{var}(\hat{p}_{Ai} - \hat{p}_{Bi}),$$

$$\text{with } \text{var}(\hat{p}_{Ai} - \hat{p}_{Bi}) = \frac{\hat{p}_{Ai}(1 - \hat{p}_{Ai})}{n_{Ai}} + \frac{\hat{p}_{Bi}(1 - \hat{p}_{Bi})}{n_{Bi}}.$$

Two-sided 95% CI will be estimated using the normal approximation to the binomial distribution via the following method,

$$d \pm [z_{1-\alpha/2} \sqrt{\text{var}(d)}].$$

Two-sided p-value for the test of the 0 difference between tofacitinib 5 mg BID and placebo groups will be calculated as:

$$p = 2(1 - \Phi(|Z|)),$$

where $\Phi(\cdot)$ is the Gaussian cumulative density function and $Z = \frac{d}{\sqrt{\text{var}(d)}}$ is the Normal

Z-test statistic.

If there is no (ie, 0) response or 100% response in any one or both of the two treatment groups for the comparison in a stratum, eg, tofacitinib 5 mg BID vs. placebo, when calculating the proportions above, 0.5 will be added to the number of responses (ie, numerator) and 1 will be added to the denominator in each treatment in that stratum corresponding to the pair of comparison for calculating the treatment difference, standard error (ie, $\sqrt{\text{var}(d)}$), 95% CI and 2-sided p-value (Agresti, 2002).⁵

When response rate of 0% or 100% is observed in both treatments in comparison and in both strata, no formal comparison will be performed. Estimated response rate of 0% or 100% will be reported as observed. Standard error will be reported as 0.

The final results will be expressed in percentages, ie, (proportions x 100)%.

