3. STUDY DESIGN

[figure not shown]
This is a Phase 3, multicenter, randomized, double-blind, placebo-controlled, efficacy and safety study of tofacitinib in subjects with active AS. Approximately 480 AS subjects will be screened globally in order that approximately 240 eligible subjects (120 per arm) will be randomized in a 1:1 ratio to tofacitinib 5 mg BID or matching placebo BID for a total of 16 weeks of blinded treatment. During the 16-week treatment period subjects will visit the clinic every two weeks (± 3 days) until the Week 4 visit and then every 4 weeks (± 7 days) until the completion of Week 16. At the Week 16 visit all subjects will be assigned to open-label tofacitinib and will visit the clinic every two months (± 7 days) until Week 48. Subjects will then return to the clinic for a Follow-up visit approximately 28 days after the Week 48 visit. There will be a total of 2 planned analyses conducted when all applicable subjects have completed their Week 16 and Week 48 (including follow-up) visits, respectively. CCI [REDACTED]

[REDACTED] The first analysis will be conducted when all applicable subjects

have completed their Week 16 visit (see [Section 9.2](#)). The investigators, subjects and sponsor study team will remain blinded to the first 16 weeks of treatment assignment through the entire duration of the trial until database release.

Randomization will be stratified by prior treatment history: (1) bDMARD-naïve and (2) Tumor Necrosis Factor inhibitor-inadequate responder (TNFi-IR) or bDMARD use (non-IR). Approximately 80% of the subjects will be bDMARD-naïve and have an inadequate response to at least 2 NSAIDs (designed as Stratum bDMARD-naïve), and the other approximately 20% of subjects who had an inadequate response to at least one but not more than 2 TNFi and have an inadequate response to at least 2 NSAIDs or bDMARD use (non-IR) [designed as Stratum TNFi-IR or bDMARD use (non-IR)]. Subjects who had prior bDMARD use (non-IR) will be eligible to participate in the study and will be included in the TNFi-IR or bDMARD use (non-IR) stratum. An inadequate response to NSAID or TNFi treatment is defined as having a treatment related adverse event or lack of response to NSAID or TNFi treatment that was administered in accordance with its labeling recommendations. The sponsor may limit enrollment of subjects with baseline hsCRP below 0.287 mg/dl to match their estimated prevalence in AS. See Figure 1.

Figure 1. Study Design Schematic

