9.1. Sample Size Determination

The primary efficacy analysis is to compare the ASAS20 response rate at Week 16 of the tofacitinib 5 mg BID and placebo via the normal approximation for the difference in binomial proportions. Assuming a placebo response rate of 40% for ASAS20 response at Week 16, a sample size of 120 per arm will yield about 89% power to detect a difference of at least 20% between tofacitinib 5 mg BID and placebo at a two-sided significance level of 5%. In the Phase 2 proof of concept trial A3921119, ASAS20 response rates at Week 12 were 63% and 40% for tofacitinib 5 mg BID and placebo, respectively.

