9.2.3. Control for Type I Error Rate

This protocol is designed to establish the superiority of tofacitinib 5 mg BID to placebo for the treatment of active AS based on the primary endpoint of ASAS20 at Week 16 in subjects who have had an inadequate response to previous treatments.

All statistical tests will be conducted at the 2-sided 5% (or equivalently 1-sided 2.5%) significance level for comparing tofacitinib 5 mg BID to placebo. Type I error will be controlled at 2-sided 5% or equivalently 1-sided 2.5%.

For the primary endpoint of ASAS20 at Week 16, if the 2-sided p value is $\leq 5\%$, the superiority of tofacitinib 5 mg BID to placebo will be declared for this primary endpoint and the primary objective of this study is met. Hypothesis testing will continue to the global family of select set of secondary endpoints stated below (*Global Type I Error Control (for the primary endpoint and a select set of secondary endpoints)*). For each of the endpoints within this family, superiority of tofacitinib 5 mg BID to placebo will be declared if statistical significance is achieved under the step-down testing procedure. In addition, three other families of hypotheses, ASAS family endpoints (*Type I Error Control for Endpoints in the ASAS Family*), ASAS20's earlier time points (*Type I Error Control for ASAS20 at Earlier Time Points*) and ASAS40's earlier time points (*Type I Error Control for ASAS40 at Earlier Time Points*) will also be tested. For each of the endpoints or time points of ASAS20/ASAS40, superiority of tofacitinib 5 mg BID to placebo will be declared if statistical significance is achieved under its respective step-down testing procedure.

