6.4. Subset (Subgroup) Analyses

6.4.1. Subgroup Analyses for Primary Endpoint of ASAS20 at Week 16

All subgroup comparisons for the primary endpoint ASAS20 at Week 16 will be made on the FAS with missing value handled by MR=NR using the on-drug data corresponding to Estimand 1 for the following comparison only:

- Tofacitinib 5 mg BID vs. Placebo.

Subgroup analysis will be performed for each of the following subgroup variables and their categories in parentheses:

- Prior treatment history - 2 categories ("bDMARD-naïve", "TNFi-IR or bDMARD Use [Non-IR]") where prior treatment history is derived from the clinical database (see [Appendix Section 9.11](#));
- Prior treatment history – 3 categories ("bDMARD-naïve", "TNFi-IR", "bDMARD Use [Non-IR]") where prior treatment history – 3 categories is derived from the clinical database. Subjects under "bDMARD Use (Non-IR)" category are not TNFi-IR and have prior bDMARD Use without IR. This subgroup analysis is only done when there is sufficient number of subjects in the "bDMARD Use (Non-IR)" category (see [Appendix Section 9.11](#));
- Geographic region – 4 regions ("North America (US and Canada)" [United States, Canada], "European Union" [Bulgaria, Czech Republic, France, Hungary, Poland], "Rest of World" [Ukraine, Russia, Australia, Turkey], "Asia" [China, South Korea]);
- Gender (Female, Male);
- Race (White, Asian, Other), when a subject selects more than one race category, this subject will be grouped to the "Other";
- Age at Baseline (<65, \geq 65 years);
- Baseline weight (<60, \geq 60 to \leq 100, >100 kg);

- Baseline Body Mass Index (BMI) (<25, ≥25 to <30, ≥30 to <40, and ≥40 kg/m²);
- AS disease symptom duration (<5, ≥5 years);
- Baseline AS disease activity (ASDAS_{CRP} <1.3 [inactive disease], ≥1.3 to <2.1 [low disease activity], ≥2.1 to ≤3.5 [high disease activity], > 3.5 [very high disease activity] units, and continuous) (van der Heijde et al. 2016; Machodo et al., 2018);⁹
- Baseline hsCRP (≤2.87, >2.87 mg/L), where 2.87 mg/L (the upper limit of normal) is defined in this study as elevated;
- Baseline smoking status (Never Smoked, Former Smoker, Current Smoker);
- Day 1 Concomitant csDMARD Use (Yes, No);
- HLA-B27 (Positive, Negative).

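### The CMH analysis of ASAS20 and ASAS40 is valid but adjusts only for prior treatment, and so may forgo a modest gain in precision from baseline hsCRP and BASDAI

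*SAP*

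**What the plan says.** SAP 5.2.1.1 estimates the difference in response proportions as a CMH-weighted risk difference, "adjusting for stratification factor of prior treatment history". That factor has two levels and is the only randomisation stratum. Protocol Section 3 plans it at about 80/20 ("Approximately 80% of the subjects will be bDMARD-naïve"). SAP 6.1.1 makes this the primary analysis of ASAS20, and SAP 6.2 carries the method over to ASAS40.

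The Schedule of Activities has hsCRP, BASDAI and the ASAS components measured at Screening and Baseline in all subjects. In the ASAS20 and ASAS40 analyses, baseline hsCRP and baseline ASDAS-CRP appear only as subgroup variables (SAP 6.4.1 and 6.4.2). No supportive analysis of the two binary endpoints adds a baseline clinical covariate. The GMMRM (SAP 5.2.1.2) has treatment, visit and their interaction; the tipping-point imputation model (SAP 9.3) adds only prior treatment. Continuous endpoints are adjusted for their own baseline value (SAP 5.2.2 and 5.2.3).

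Baseline hsCRP appears in two other places. Protocol Section 3 says "The sponsor may limit enrollment of subjects with baseline hsCRP below 0.287 mg/dl to match their estimated prevalence in AS". SAP 6.4.1 splits a subgroup at the same threshold, "where 2.87 mg/L (the upper limit of normal) is defined in this study as elevated".

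**The concern.** When a baseline variable predicts response, leaving it out of the analysis leaves the confidence interval for the treatment difference wider than it need be. The estimate also does not take account of any chance difference between arms in that variable. Here the candidate variables are already scheduled for everyone before dosing, so using them needs no new data collection.

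ASAS20 decides the trial. ASAS40 is second in the step-down sequence (Protocol 9.2.3); if it fails, the six endpoints below it are all non-significant. A small gain in precision on these two endpoints is therefore worth having if it exists.

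**Working it through.** **Inputs from the documents**
- Test level: "All statistical tests will be conducted at the 2-sided 5% (or equivalently 1-sided 2.5%) significance level" (Protocol 9.2.3).
- Placebo rate: "Assuming a placebo response rate of 40% for ASAS20 response at Week 16" (Protocol 9.1).
- Effect, size and power: "a sample size of 120 per arm will yield about 89% power to detect a difference of at least 20" percent (Protocol 9.1), so 60% against 40% with 120 per arm.
- Allocation: "will be randomized in a 1:1 ratio to tofacitinib 5 mg BID" or placebo (Protocol 3), with 96 and 24 per arm by stratum (Protocol 5.1).
- Target quantity: the difference in response rates (SAP 2.1.1, Estimand 1).

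**The plan's own figure.** With the unpooled variance of SAP 5.2.1.1, SE = sqrt(0.24/120 + 0.24/120) = 0.0632. Power = Φ(0.20/0.0632 − 1.96) = 88.5%. The pooled form gives 87.7%. Both agree with the stated value of about 89%.

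**Adding baseline covariates.** Let R² be the share of response variance within arms that the added covariates explain. In large samples the variance of a covariate-standardised risk difference is about (1 − R²) times the unadjusted variance, so SE = 0.0632 × sqrt(1 − R²). The equivalent total sample size is 240/(1 − R²). The documents give no R²; every value below is assumed.

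| Assumed R² | SE (points) | 95% CI half-width (points) | Power | Equivalent total N |
|---|---|---|---|---|
| 0 | 6.32 | 12.4 | 88.5% | 240 |
| 0.02 | 6.26 | 12.3 | 89.2% | 245 |
| 0.05 | 6.16 | 12.1 | 90.0% | 253 |
| 0.10 | 6.00 | 11.8 | 91.5% | 267 |

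**Check by simulation.** There were 4000 trials per setting, with 96 and 24 per arm by stratum, the stratum itself not prognostic, and one normally distributed covariate. The planned CMH was compared with logistic regression standardised to a risk difference, using an influence-function SE.

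| R² | Power, CMH | Power, standardised |
|---|---|---|
| 0 | 87.8% | 87.0% |
| 0.015 | 87.6% | 88.0% |
| 0.054 | 88.6% | 89.3% |
| 0.109 | 88.3% | 91.2% |

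The Monte Carlo SE of one power figure is about sqrt(0.88 × 0.12/4000) = 0.5 points. Type I error was 5.0 to 5.9% for CMH and 4.5 to 5.8% for the standardised estimator (Monte Carlo SE about 0.35 points).

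**ASAS40.** The documents give no planning rates, so these are assumed too. Power at R² of 0, 0.05 and 0.10 is:
- 20% against 35%: 75.2, 77.3 and 79.5%;
- 15% against 30%: 80.7, 82.7 and 84.6%;
- 20% against 40%: 93.4, 94.5 and 95.5%.

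**Why not more CMH strata.** Adding hsCRP as a stratum (four strata, assuming about 31% low) produced a 0% or 100% cell in 10 to 35% of simulated trials. Adding a 50/50 disease-activity split as well (eight strata) raised this to 80 to 94%. Each such cell triggers the 0.5 correction in SAP 5.2.1.1.

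**The case against.** The strongest reply is that nothing here is an error. The CMH estimator respects the randomisation stratum, targets the Estimand 1 risk difference, reproduces the planned power and holds its type I error. Randomisation makes the estimate unbiased, and its confidence interval already allows for chance imbalance. Baseline hsCRP, BASDAI and the four components are tabulated by arm (SAP 6.5.1), and the components are analysed with baseline adjustment in support of the primary endpoint (SAP 6.1.2). All of this stands.

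A reader might infer that hsCRP is known to be prognostic because enrolment may be limited by it and a subgroup is formed on it. The documents do not support that. The cap is optional and its stated purpose is to match prevalence. The subgroups are there to check consistency of the effect (SAP 6.4.1), which is a different matter from predicting response.

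Nor does adjustment of the continuous endpoints settle the question, since each is adjusted for its own baseline and a responder variable has none. SAP 4.4.1 restricts the ASDAS responder endpoints by baseline so that there is room to respond, which hints that the starting level can matter. It gives no size, however, and entry at BASDAI of at least 4 narrows that covariate's range.

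The change is also more than one line of text. Protocol Section 9 requires an amendment for a major change to the primary analysis, and the on-study, per-protocol and tipping-point analyses all use CMH. These are real but small specification tasks.

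**Conclusion.** The point holds as an efficiency improvement to a valid plan. The primary and key secondary analyses use one binary factor and may forgo a modest gain from baseline values already collected. For ASAS20 the approximate gain is 0.7, 1.5 or 3.0 power points at an assumed R² of 0.02, 0.05 or 0.10. The simulation supports the direction: 0.7 points near 0.05 and about 3 near 0.11.

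Two stronger readings are tempting. One is that precision is certainly being lost; without an R² in the documents, that cannot be established. The other is that adjustment would be free. It needs an amendment, and at R² = 0 the simulated power was slightly lower. The recommendation rests on that possible loss being small beside the possible gain.

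**What to change.** Before unblinding, amend Protocol 9.2.1 and SAP 5.2.1.1, 6.1.1 and 6.2 as follows.

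- Estimate the same Week 16 risk difference by logistic regression with treatment, prior-treatment stratum, baseline ln(hsCRP) and baseline BASDAI, standardised over the FAS. This keeps the Estimand 1 summary, which a conditional odds ratio would not. SAP 9.2.4 sets hsCRP to 0.199 mg/L in connection with the assay's quantification limit, so the logarithm is defined there.
- Name the standard error: robust or delta-method.
- Use the last non-missing pre-dose value of each covariate, as SAP 9.4 already defines Baseline, with a simple imputation if none exists. No FAS subject is then dropped.
- Keep the on-drug and MR=NR rules.
- Apply the same estimator in the on-study, per-protocol and tipping-point analyses. Confirm that earlier visits follow, since SAP 6.1.1 and 6.2 tie them to the primary method.
- Keep the stratified CMH as the sensitivity analysis and as the pre-specified fallback for non-convergence.

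The Phase 2 trial of about 200 subjects (Protocol 1.2.5) could be used to gauge R² first. It is a better source than blinded data from this trial, because Protocol 7.2.3 withholds post-screening hsCRP from the study team.

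The cost is a protocol and SAP amendment, covariates and their form fixed in advance, and a negligible power loss if they turn out not to be prognostic. No new data are needed.

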5.2.1.2. Generalized Marginal Model for Repeated Measures (GMMRM)

As a supportive analysis of ASAS20 (or ASAS40) for Estimand 3 (Section 2.1.1) scheduled to be collected multiple times during the first 16 weeks of placebo-controlled period (Weeks 2, 4, 8, 12 and 16) of the study, a generalized marginal linear model for repeated measures (GMMRM) will be used. This model will have fixed effects for treatment, visit (discrete), and treatment-by-visit interaction; the dependent variable will be the logit of the probability of ASAS20 (or ASAS40) response. Note that the model includes fixed effects of treatment, visit, and treatment-by-visit interaction only to ensure the estimated response rates and the treatment difference have a population average or marginal interpretation. A common autoregressive of order 1 [AR(1)] variance-covariance matrix for the two treatment groups will be used to model the variability among observations within a subject. If AR(1)

matrix fails to converge, compound symmetry will be attempted. The parameters of the model will be estimated with pseudo-likelihood type methods. Simulations investigating generalized linear models (GLM) for correlated binary data fit with generalized linear mixed effect model indicate good performance as measured by Type I error, CI coverage and bias even in the presence of data that is MAR (Liu and Zhan, 2011).⁶ From this model, one can obtain estimates of response rates for each treatment group at each time point (at Week 16 and prior) as well as inferential comparisons between treatment groups (odds ratio [OR], 95% CI, and p-value). In the unlikely event that a response rate is 0 or 100% at a particular visit for a treatment group that may lead to convergence issues, data from that visit for both treatment groups will be removed from the model fitting in order to overcome any numerical difficulty.

5.2.1.3. Tipping Point Analysis

A method to analyze the longitudinal data of a binary endpoint measured during the placebo-controlled period (eg, ASAS20 [or ASAS40] response rates at Weeks 2, 4, 8, 12 and 16) under the missing not at random (MNAR) assumption is called the tipping point analysis. This analysis is used as a supportive analysis for the primary endpoint of ASAS20 and the key secondary endpoint of ASAS40 both at Week 16. It assesses the robustness of the binary data to potential deviations from the missing at random (MAR) assumption for both tofacitinib 5 mg BID and placebo groups and it is based on multiple imputation (Yan, Lee and Li, 2009; Ratitch, O’Kelly and Tosiello, 2013).^{7,8}

In this tipping point analysis, a single saturated generalized linear mixed effect model is used as the imputation model. The normal approximation of the difference in binomial proportions using the CMH method adjusting for prior treatment history at randomization ("bDMARD-naïve" vs. "TNFi-IR or bDMARD Use [Non-IR]") is used as the analysis model, which is the same as the method of analyzing response-type endpoint at a single time point described in [Section 5.2.1.1](#). The generalized linear mixed effect model includes the fixed effects of treatment, visit, treatment-by-visit interaction, prior treatment history at randomization ("bDMARD-naïve" vs. "TNFi-IR or bDMARD Use [Non-IR]"), and a latent subject-level random effect. The logit link is used to model the ASAS20 (or ASAS40) response rate as dependent variable for all visits. Estimation of the model parameters is performed under the Bayesian framework using Markov Chain Monte Carlo (MCMC) methods. Only the available on-drug data (see [Appendix Section 9.1](#)) without imputation are included in this generalized linear mixed effect model to estimate the model parameters.

Imputation of missing ASAS20 (or ASAS40) response is performed only at Week 16 based on the predictive distribution of the generalized linear mixed effect model. Under missing not at random (MNAR) assumption, a fixed MNAR quantity (favorable or unfavorable) will be applied to the probability of the ASAS20 (or ASAS40) response at Week 16 for subjects with missing response in the tofacitinib 5 mg BID group and placebo group independently (ie, the analysis will be two-dimensional applied to both tofacitinib 5 mg BID and placebo). A series of fixed quantities will be applied to the probability of the ASAS20 (or ASAS40) response at Week 16 for subjects with missing response in the tofacitinib 5 mg BID group or placebo group independently to assess when the conclusion might change (ie, tipping). A scenario included in the tipping point analysis framework is an analysis under MAR, if there is no fixed quantity applied to the mean of the missing response for subjects in the tofacitinib

5 mg BID group and placebo group. The Rubin's rules (Rubin, 1987)² will be used to combine the results of multiple imputed samples for inference. More detailed step-by-step descriptions are provided in the [Appendix \(Section 9.3\)](#).

5.2.2. Analyses for Continuous (Repeated) Data

Repeated measures data for continuous or order-categorical (analyzed as continuous) endpoints will be analyzed as change from baseline as appropriate with a mixed model for repeated measures (MMRM) that includes fixed effects of treatment group, visit, treatment-group by visit interaction, stratification factor (ie, prior treatment history: "bDMARD-naïve" vs "TNFi-IR or bDMARD Use [Non-IR]") at randomization, stratification-factor by visit interaction, baseline value, and baseline-value by visit interaction. A common unstructured variance-covariance matrix will be used, provided the model converges, otherwise an alternative covariance structure, eg, heterogeneous compound symmetry (CSH), will be attempted. The Kenward-Roger degrees of freedom approximation will be used. This model is referred to as MMRM. Comparison of tofacitinib 5 mg BID to placebo (providing least squares means [LSM] of the treatments, LSM of the treatment difference, 2-sided p-value and 95% CI) at each time point during the first 16 weeks will be generated using this MMRM. Comparisons of tofacitinib 5 mg BID and placebo → tofacitinib 5 mg BID for visits after Week 16 through Week 48 are also reported from the same model. For each endpoint, the number of subjects by treatment group in the FAS, the number of subjects by treatment group included in the MMRM and the number of subjects by treatment group evaluable at each of the visits are also to be reported. If the Baseline is missing or if there are no post-baseline measurements, the subject will be excluded from this analysis (see [Section 4.1](#)).

